4.2. Primary Endpoint(s) Analyses

The primary objectives of Part 3 are:

- To assess the safety and tolerability of oral administration of GSK3965193 monotherapy
- To evaluate PD effect of GSK3965193 monotherapy in PLWCHB

4.2.1. Definition of endpoints

The following endpoints will be assessed:

- Occurrence of AEs and SAEs
- Occurrence of clinically significant changes in laboratory values (hematology, clinical chemistry, and urinalysis), vital sign parameters, 12-lead ECG parameters, and sensory nerve conduction parameters
- Maximum reduction of HBsAg levels from baseline CCI

4.2.2. Main analytical approach

The safety analyses will be based on the safety set, unless otherwise specified.

All the PD analyses will be based on PD set, unless otherwise specified.

4.2.2.1. Adverse events, Serious Adverse events, and Adverse Event of Special Interest (AESI)

An adverse event (AE) is considered study treatment emergent if the AE onset or worsen date is on or after Study treatment start date.

For this part, TEAE will be derived as following:

- TEAE for GSK/Placebo = Date of First GSK/Placebo Dose \leq Date of AE Onset/Worsening \leq Date of GSK/Placebo Last Dose + 7 Days

Any AE which occurs outside the above-mentioned time window will not be considered as TEAE due to GSK3965193 or placebo.

All AE summaries will be based on treatment emergent events and summarised by treatment. Serious AE (SAE) summaries will be also based on all treatment emergent SAEs. All non-treatment emergent AEs and SAEs will be listed. The following displays for Adverse events will be generated:

Table 5 Details of Adverse Event Summaries

	GSK3965193 Monotherapy
AEs	Overview of all Adverse Events
	Summary of Treatment Emergent Adverse Events by System Organ Class and Preferred Term
	Summary of Treatment Emergent Adverse Events Leading to Treatment Discontinuation by System Organ Class and Preferred Term
	Summary of Treatment Emergent Adverse Events by System Organ Class and Preferred Term and Maximum Grade
	Summary of Drug-Related Treatment Emergent Adverse Events by System Organ Class and Preferred Term and Maximum Grade
	Summary of Treatment Emergent Non-Serious Adverse Events by System Organ Class and Preferred Term (Number of Subjects and Occurrence)
	Summary of Common ($\geq 10\%$) Treatment Emergent Non-Serious Adverse Events by Overall Frequency
SAEs	Summary of Serious Treatment Emergent Adverse Events by System Organ Class and Preferred Term and Maximum Grade
	Summary of Serious Treatment Emergent Adverse Events Leading to Treatment Discontinuation by System Organ Class and Preferred Term

	GSK3965193 Monotherapy
	Summary of Serious Fatal and Non-Fatal Drug-Related Treatment Emergent Adverse Events by Overall Frequency
	Summary of Serious Treatment Emergent Adverse Events by System Organ Class and Preferred Term (Number of Subjects and Occurrences)
AESI	Summary of Adverse Events of Special Interest by System Organ Class and Preferred Term

AEs will be coded using the latest version of Medical Dictionary for Regulatory Affairs (MedDRA) coding dictionary, to give a Preferred Term (PT) and a System Organ Class (SOC). These PTs and SOCs will be used when summarising the data. The severity of AEs and SAEs will be determined by the investigator according to the [Division of AIDS DAIDS, 2017] grading system Version 2.1, unless specified otherwise in the protocol.

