#### **8.3.1. Time Period and Frequency for Collecting AE and SAE Information**

- All SAEs will be collected from the signing of the ICF until the final follow-up visit at the time points specified in the SoA (Section 1.3). However, SAEs that occur prior to the first administration of investigational medicinal product should be recorded only if assessed as related to study participation (e.g., protocol-mandated procedures or invasive tests).
- All AEs will be collected from the start of intervention until the final follow-up visit at the time points specified in the SoA (Section 1.3).
- Medical occurrences that begin before the start of study intervention but after obtaining informed consent will be recorded as Medical History/Current Medical Conditions, not as AEs.
- All SAEs will be recorded and reported to the sponsor or designee immediately and under no circumstance should this exceed 24 hours, as indicated in Section 10.3 (Appendix 3). The investigator will submit any updated SAE data to the sponsor within 24 hours of it being available.
- Investigators are not obligated to actively seek information on AEs or SAEs after the conclusion of the study participation. However, if the investigator learns of any SAE, including a death, at any time after a participant has been discharged from the study, and he/she considers the event to be reasonably related to the study intervention or study participation, the investigator must promptly notify the sponsor.

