6.2.2. Study Period

Assessments and events will be classified according to the time of occurrence relative to the study intervention period.

Table 17 Study Period Definition

Study Intervention Period	Definition
Pre-GSK3965193/Placebo Period	Date < GSK3965193/Placebo Start Date
GSK3965193/Placebo Monotherapy Period	GSK3965193/Placebo Start Date ≤ Date < GSK3965193/Placebo Last Date
GSK3965193/Placebo Off treatment period	GSK3965193/Placebo last dose ≤ Date < GSK3965193/Placebo Last date + 14 days
GSK3965193/Placebo Follow-up	GSK3965193/Placebo Last date + 14 days ≤ Date if the participant doesn't take part in the optional bepirovirsen extension or GSK3965193 Off treatment period ≤ Date < Bepirovirsen Treatment Period Start date
Bepirovirsen Treatment Period	Bepirovirsen Treatment Start date ≤ Date ≤ Bepirovirsen End date
Bepirovirsen Treatment Follow-up	Date > Bepirovirsen Treatment End date

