Adverse Events	
 Partial dates for AE recorded in the CRF will be imputed using the following conventions: 
 
 Missing start day	 
If study intervention start date is missing (i.e. participant did not start study intervention), then set start date = 1st of month.
 
Else if study intervention start date is not missing:
 
 If month and year of start date = month and year of study intervention start date, then 
 If stop date contains a full date and stop date is earlier than study intervention start date, then set start date= 1st of month. Else set start date = study intervention start date. 
Else set start date = 1st of month.
 	
 
 Missing start day and month	 
If study intervention start date is missing (i.e. participant did not start study intervention), then set start date = January 1.
 
Else if study intervention start date is not missing:
 
 If year of start date = year of study intervention start date, then 
 If stop date contains a full date and stop date is earlier than study intervention start date, then set start date = January 1. Else set start date = study intervention start date. 
Else set start date = January 1.
 	
 
 Missing end day	A '28/29/30/31' will be used for the day (dependent on the month and year).	
 
 Missing end day and month	No Imputation	
 
 	Missing start day	
If study intervention start date is missing (i.e. participant did not start study intervention), then set start date = 1st of month.
 
Else if study intervention start date is not missing:
 
 If month and year of start date = month and year of study intervention start date, then 
 If stop date contains a full date and stop date is earlier than study intervention start date, then set start date= 1st of month. Else set start date = study intervention start date. 
Else set start date = 1st of month.
	Missing start day and month	
If study intervention start date is missing (i.e. participant did not start study intervention), then set start date = January 1.
 
Else if study intervention start date is not missing:
 
 If year of start date = year of study intervention start date, then 
 If stop date contains a full date and stop date is earlier than study intervention start date, then set start date = January 1. Else set start date = study intervention start date. 
Else set start date = January 1.
	Missing end day	A '28/29/30/31' will be used for the day (dependent on the month and year).	Missing end day and month	No Imputation

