4.4.2. Adverse Events

An adverse event (AE) is considered study intervention emergent if the AE onset date is on or after study intervention start date. This definition of study intervention emergent AE is applicable only for Part 2A.

For Part 1 and Part 2B, an AE is considered study intervention emergent if the AE onset date is on or after study intervention start date (i.e., Day 1) till CCI after study intervention administration. Any AE which starts post Day 5 of study intervention administration will not be considered as study intervention emergent AE.

All AE summaries will be based on study intervention emergent events unless otherwise specified. SAE summaries will be based on all SAEs reported regardless of whether they meet the definition of study intervention emergent or not.

Adverse event (AE) will be coded using Medical Dictionary for Regulatory Activities (MedDRA) central coding dictionary. Adverse event analysis will be based on GSK Core Data Standards.

The following displays for Adverse events will be generated: All Adverse Events by System Organ Class and Preferred Term, AEs leading to withdrawal, Adverse Event by maximum severity grade, Treatment related Adverse Events, Treatment related AEs leading to withdrawal, Treatment relates AEs leading to death, Serious and non-serious Adverse Events and Serious Adverse Events. Further details of the planned displays will be given in OPS.

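### Part 3 AE and SAE tables for GSK3965193/placebo stop 7 days after the last dose, so events on days 8 to 14 of the 2-week washout are listed but not tabulated as treatment emergent

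*SAP*

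**What the plan says.** SAP (Part 3) 4.2.2.1 opens with a general definition that has no upper limit: an AE is emergent if it starts or worsens on or after treatment start. It then gives the derivation specific to this part, whose upper limit is "Date of GSK/Placebo Last Dose + 7 Days". It adds: "Any AE which occurs outside the above-mentioned time window will not be considered as TEAE due to GSK3965193 or placebo". Two sentences set the scope of the tables: "All AE summaries will be based on treatment emergent events and summarised by treatment" and "Serious AE (SAE) summaries will be also based on all treatment emergent SAEs". AEs and SAEs that are not emergent go to listings.

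SAP 4.3.1.2.3 opens the bepirovirsen window at the first bepirovirsen dose, with no upper limit.

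Protocol 4.2.3 places a 2-week washout before optional bepirovirsen and gives participants who decline it 2 weeks of off-treatment follow-up. Protocol 8.3.1 says: "All AEs will be collected from the start of intervention until the final follow-up visit". Incidence of AEs and SAEs is a primary endpoint of Part 3 (Protocol Section 3; SAP 1.1 and 4.2.1).

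The Parts 1/2 SAP (4.4.2) took a different line on serious events: "SAE summaries will be based on all SAEs reported regardless of whether they meet the definition of study intervention emergent or not".

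Two related rules sit in SAP Appendix 2. Table 17 (6.2.2) ends the monotherapy period with "Date < GSK3965193/Placebo Last Date" and starts the off-treatment period on the last dose date. The partial-date rule for AEs (6.2.6) turns on one condition: "If month and year of start date = month and year of study intervention start date, then".

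**The concern.** The two emergent windows in Part 3 do not meet. Between the close of the first and the opening of the second lies the second half of the washout, when participants are still under observation and AEs are still being recorded. A serious event in that interval is collected for a primary endpoint and then left out of the SAE tables by rule. The Part 3 SAP gives no reason, and its list of changes from the protocol (Table 12) does not mention the window.

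SAEs matter most here. They are few, a reader of the report looks for them in the tables, and the earlier parts of the same study tabulated all of them. The Part 3 list of planned AE displays (Table 5) also has no separate deaths summary, whereas the bepirovirsen list (Table 10) has one.

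The Table 17 and partial-date rules raise a related question: to which treatment period does a given day or event belong?

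**Working it through.** No sample size, power or event rate is involved. The check places each study day under the SAP's own inequalities.

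**Inputs**
- Upper limit of the GSK3965193/placebo window: last dose + 7 days, inclusive (SAP 4.2.2.1).
- Start of the bepirovirsen window: first bepirovirsen dose (SAP 4.3.1.2.3).
- Washout, or follow-up for those who decline bepirovirsen: 14 days (Protocol 4.2.3).
- Last dosing day: Day 28. This is inferred from the last Part 3 PK day in Protocol 9.4.7, because the schedule is redacted.
- Bepirovirsen start: Day 43 (Protocol 7.1).

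**Emergent windows**
- The GSK3965193/placebo window closes on Day 28 + 7 = Day 35.
- The bepirovirsen window opens on Day 43.
- Days in neither window: Days 36 to 42, which is 7 days. 7/14 = 50% of the washout.
- Participants who decline bepirovirsen are followed to Day 28 + 14 = Day 42 and have the same 7 uncovered days.
- Early stopper, with last dose on Day 10 as an illustration: the window closes on Day 17, and Days 18 to 24 (days 8 to 14 after the last dose) are uncovered.
- The 7-of-14 result does not depend on Day 28. It needs only the + 7 limit and the 2-week washout.

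**Table 17, last dose on Day 28**

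| Day | Period under the SAP's inequalities |
|---|---|
| 27 | Monotherapy |
| 28 (last dosing day) | Off treatment |
| 29 to 41 | Off treatment |
| 42 | Follow-up |
| 43 | Bepirovirsen |

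The bepirovirsen row of the same table includes its end date, so the two treatment periods are closed by different rules. TEAE counts do not change, because the TEAE formula includes the last dose date.

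**Partial dates.** Suppose the start date in the rule is read as the GSK3965193/placebo start. Bepirovirsen begins on Day 43, which is calendar day d of its month. Day 1 is 42 days earlier, so it always lies in an earlier month. An AE with only month and year known, in the month bepirovirsen starts, is then imputed to the 1st, which is study Day 43 − (d − 1) = 44 − d.
- d = 1: Day 43, inside the bepirovirsen window.
- d = 2 to 8: Days 42 to 36, in neither window.
- d = 9 to 31: Days 35 to 13, inside the GSK3965193/placebo window.

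On this reading the usual result is attribution to GSK3965193/placebo. Less often, the event falls in no window.

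**The case against.** The strongest reply is that 7 days is a sensible exposure-based limit. The Parts 1/2 SAP capped the window for Parts 1 and 2B and cited a short half-life in its version history. Protocol 5.1.1 also uses 7 days after the last GSK3965193 dose for contraception. This stands as far as the length of the AE window goes. It is not stated in the Part 3 SAP, however, and that earlier rationale was not applied to Part 2A, the repeat-dose part, which had no upper limit. Nor does it explain dropping SAEs from tables, since the Parts 1/2 SAP kept all SAEs even where it capped the AE window.

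Second, nothing is lost: non-emergent events are listed, and Protocol 9.4.5 relies on individual data as well as descriptive statistics. The cohort also looks small. SAP 1.1.3 equates more than 20% with 4 or more participants, so 4/N > 0.20 gives N < 20 and 3/N ≤ 0.20 gives N ≥ 15. Listings of that size can be read case by case. This lowers the stakes, but it does not put the events into the by-arm incidence.

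Third, a reader might infer that these events leave every summary table. The documents do not establish that. In Table 5 the overall AE overview and the AESI display lack the treatment-emergent label, although the governing sentence covers all AE summaries, so their status is unclear. Neuropathy and neurocognitive events are AESIs and fall in one of those displays. Nerve conduction, neuropathy score, laboratory, vital-sign and ECG summaries do not use the window.

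Fourth, a reader might see a conflict with the treatment-policy strategy in Protocol Table 1. That strategy governs data after discontinuation. The window sets the endpoint's time frame and is the same for completers and early stoppers. Likewise, the open-ended first sentence of 4.2.2.1 is general, and the derivation for this part controls.

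Fifth, study intervention can be read to include bepirovirsen, so the partial-date result depends on interpretation.

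**Conclusion.** The point holds in a limited form. AEs and SAEs that start on days 8 to 14 after the last GSK3965193/placebo dose, 7 of 14 days, fall in neither emergent window and are guaranteed only a listing. The window length for AEs is arguable and needs a stated reason. Leaving SAEs out of the tables is harder to defend, given the Parts 1/2 rule.

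The number of events affected cannot be given. A reader might turn 7 of 42 days into about one AE in six, but that needs a constant event rate through the washout. The documents give no such rate, and a short half-life argues against it.

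The Table 17 error is real and affects only data classified by period. A reader might infer that the partial-date rule drops bepirovirsen-period events. It is better described as an ambiguity that, on one reading, mostly misattributes them to GSK3965193/placebo. The day counts for that and for Table 17 assume a last dose on Day 28 and bepirovirsen on Day 43.

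**What to change.** 1. Summarise all SAEs by arm from the first GSK3965193/placebo dose to the day before the first bepirovirsen dose, or to final follow-up for those not continuing, regardless of the 7-day window.
2. For AEs, choose one of two options: extend the emergent window to the same limit, or keep last dose + 7 days with its rationale written in and add a by-arm table of AEs over the full washout. State whether the overall AE overview and the AESI display use the window.
3. In Table 17, change the monotherapy upper bound to ≤ and begin the off-treatment period on the following day.
4. In the partial-date rule, name the start date that applies to AEs in the bepirovirsen period.

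With last dose on Day 28 and bepirovirsen on Day 43, the limit in item 1 covers Days 36 to 42 and leaves no gap. The cost is SAP wording, reprogramming of the emergent and period flags, and slightly higher AE and SAE counts. No new data are needed.

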4.2.2.2. Laboratory Data, Vital Signs and ECG Data

For laboratory (haematology, clinical chemistry, urinalysis), vital signs, and ECG data, the following will be summarized:

1. For selected parameters, values outside the Potential Clinical Importance (PCI) range at each visit will be summarized as clinically significant. All other parameters will be summarized based on normal range values.
2. Change from baseline values at each visit.

Additional ECG summaries:

- Summary of Maximum QTc Values Post-Baseline Relative to Baseline by Category
- Summary of Maximum Increase in QTc Values Post-Baseline Relative to Baseline by Category

Laboratory parameters will be graded using [DAIDS, 2017] grading system Version 2.1, Table for Grading the Severity of Adult and Paediatric Adverse Events.

RAPIDO listings will be generated for the laboratory parameters.

4.2.2.3. Sensory Nerve Conduction (SNCV), Nerve Function Examination, Cognitive assessment

Sensory nerve conduction test and nerve function examination will be performed at Baseline, CCI. Nerve function will be conducted using Toronto Clinical Neuropathy Scoring System (TCNS).

Following summaries will be provided for SNCV and nerve function examination –

- Summary of Change from Baseline in Sensory Nerve Conduction by Visit and Treatment

- Summary of Nerve Conduction Shifts from Baseline
 - Incidents of participants having 25% decrease in nerve conduction velocity.
 - Incidents of participants having 50% decrease in nerve conduction amplitude.
- Summary of Change from Baseline in Nerve Function Examination by Visit and Treatment using TCNS
- Summary of Nerve Function Exam Shifts from Baseline
 - Incidents of participants having change from baseline ≥ 2 -point increase with respect to the total score will be reported.
 - Incidents of participants having a ≥ 4 -point increase.

Cognitive assessment will be conducted in case of neurocognitive symptoms observed using Modified Mini-Mental Status Exam (MMSE) and RAPIDO listings will be provided.

4.2.2.4. Pharmacodynamic (HBsAg)

Unless otherwise specified, all PD analysis will be reported using PD analysis set.

CCI

CCI

CCI

CCI

CCI

.Following summaries will be provided -

- Summary of Change from Baseline in HBsAg by Visit and Treatment
- Summary of Time to Maximum Reduction in HBsAg

To estimate the mean of maximum reduction of serum HBsAg levels from baseline CCI, a Bayesian approach will be used. This approach will use Gumbel distribution $F(x, \alpha, \beta)$ as the likelihood function for the maximum \log_{10} HBsAg reduction.

For each participant, a non-informative prior will be used with α and β is assumed to be known. The posterior distribution for α will be derived and the posterior probabilities $P(\text{mean of maximum } \log_{10} \text{ HBsAg reduction} \geq \text{cutoff} \mid \text{data})$ will be obtained from the posterior distribution.

CCI

CCI

CCI

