**5.1.3. Additional Inclusion Criteria for PLWCHB (Parts 3 and 4)**

TYPE OF PARTICIPANT AND DISEASE CHARACTERISTICS	
6.	Participants who have documented chronic HBV infection $\geq 6$ months prior to screening
7.	Participants currently receiving stable nucleos(t)ide analog (NA) therapy (e.g., tenofovir disoproxil, tenofovir alafenamide, entecavir). "Stable" is defined as no changes to the nucleos(t)ide regimen for at least 6 months prior to screening and with no planned changes to the regimen for the duration of the study
8.	Plasma or serum HBsAg concentration $> 100$ IU/mL
9.	Plasma or serum HBV DNA concentration $< 90$ IU/mL
10.	HBeAg positive or negative
11.	ALT $\leq 2$ x the upper limit of normal (ULN)

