1.1.1. Primary Estimand

The primary clinical question of interest is: What is the difference in maximum reduction of HBsAg from baseline CCI in GSK3965193 vs. placebo in participants living with chronic hepatitis B infection, prior to prohibited medication use or temporary/permanent discontinuation of treatment?

Attributes of Estimand:

Variable/Endpoint	Treatment	Population	Population Summary
Maximum reduction of serum HBsAg levels from baseline CCI CCI CCI CCI	GSK3965193 and Placebo	PLWCHB treated on stable nucleos(t)ide analog (NA) therapy	Mean of maximum reduction in change from baseline over all patients in GSK3965193 and Placebo. Treatment difference (GSK3965193 – Placebo).

Intercurrent Event			Strategy	
Intercurrent Event	Details on the Intercurrent Event	Decision on the usage of data	Strategy	Rationale
Temporary or permanent discontinuation of dosing	Temporary or permanent discontinuation of IP dose include any of the following occurrences: 
 Missing 2 or more consecutive doses Permanent discontinuation from treatment Permanent discontinuation from study 	Data from Day 1 (post randomization) until start of temporary discontinuation or permanent discontinuation.	While on-treatment	Data will only be used until the start of temporary discontinuation or date of permanent discontinuation. This is to capture that the participant could not tolerate the study treatment as planned.

CCI

CCI

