- Compute the change in log10 HBsAg values from baseline for each post-baseline visit as: Log10 HBsAg at post baseline - Log10 HBsAg at baseline
- Maximum reduction in log10 HBsAg value is the minimum value of the calculated change from baseline at any post-baseline visit within the specified timeframe (CCI)

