4.1.3. Baseline Definition

Unless otherwise stated, if baseline data is missing, no derivation will be performed, and baseline will be set to missing.

Table 3 Baseline definition of different parameters for GSK3965193 Monotherapy

Parameters	Study Assessment Visit considered as Baseline for GSK3965193 monotherapy	Derivation of Baseline
12-Lead ECG	Pre-dose Day 1	Average of triplicate ECG measurements
Vital Sign	Pre-dose Day 1	Average of triplicate Vital Sign parameters measurement
Sensory nerve conduction test (SNCV)	Screening, Day -1	The best measurement out of Screening and Day -1 will be considered as baseline, where best being the higher measurement.
Nerve Function	Screening, Day -1	The worst measurement out of Screening and Day -1 will be considered as baseline, where worst being the higher total score.
Cognitive assessment	Day -1 or Prior to dosing Day 1 (whichever is latest)	Single measurement
Clinical laboratory (Chemistry and hematology)	Day -1 or Prior to dosing Day 1 (whichever is latest)	Single measurement
Liver Function	Day -1 or Prior to dosing Day 1 (whichever is latest)	Single measurement
Prothrombin time (PT), international normalized ratio	Day -1 or Prior to dosing Day 1 (whichever is latest)	Single measurement
Urinalysis	Day -1 or Prior to dosing Day 1 (whichever is latest)	Single measurement

Parameters	Study Assessment Visit considered as Baseline for GSK3965193 monotherapy	Derivation of Baseline
Urine albumin-creatinine ratio (ACR)	Day -1 or Prior to dosing Day 1 (whichever is latest)	Single measurement
HBsAg, HBV DNA	Prior to dosing Day 1	Single measurement
CCI	CCI	CCI

Table 4 Baseline definition of different parameters in optional Bepirovirsen monotherapy

Parameters	Study Assessment Visit considered as Baseline for Optional Bepirovirsen arm	Derivation of Baseline
Vital Sign	CCI	Single measurement
Clinical laboratory (Chemistry and hematology)		
Urinalysis	CCI	Single measurement
Urine albumin-creatinine ratio (ACR)		
HBsAg, HBV DNA		

Note: Unscheduled visits prior to dosing will also be considered while deriving baseline.

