6.1.2. Demographic and Baseline Characteristics

The demographic characteristics including age, gender, ethnicity, height/weight at screening and race will be summarized with descriptive statistics. In addition, the following age categories 18-33, 34-49, 50-65 and HBsAg categories at screening will be also presented for GSK3965193 monotherapy arm. Demographic data will be summarized using Safety Analysis Set.

For Optional Bepirovirsen Extension arm demographic characteristics including sex, age, ethnicity, race, height, and weight will be summarized with descriptive statistics using OBE set. Hepatitis B characteristics, as collected on the Hepatitis B Disease Characteristics eCRF, will be summarized using descriptive statistics and will be listed.

Past medical conditions and current medical conditions as of screening will be summarized respectively.

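### As visible, the Part 3 primary HBsAg model has no baseline HBsAg term and no adjusted sensitivity analysis is planned, so chance baseline imbalance in a very small trial is handled only by subtraction

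*SAP*

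**What the plan says.** - **Model (SAP 4.2.2.4).** The stated aim is "To estimate the mean of maximum reduction of serum HBsAg levels from baseline" by a Bayesian approach. "This approach will use Gumbel distribution", with parameters α and β, as the likelihood for the maximum log10 HBsAg reduction. The next sentence begins "For each participant, a non-informative prior will be used with" and goes on to say that β is taken as known. Only α receives a posterior, from which the probability that the mean reduction reaches a cutoff is read. No covariate is named.
- **Endpoint (SAP 4.1.1).** The derivation includes the step "Compute the change in log10 HBsAg values from baseline for each post-baseline visit", and the most negative change is kept. Baseline therefore enters once, by subtraction.
- **Baseline (SAP 4.1.3).** The table titled "Baseline definition of different parameters for GSK3965193 Monotherapy" gives HBsAg a single pre-dose Day 1 value.
- **Estimand (SAP 1.1.1).** The population summary includes the difference in mean maximum reduction, GSK3965193 minus placebo.
- **Other uses of baseline HBsAg.** SAP 6.1.2 says "HBsAg categories at screening will be also presented for GSK3965193 monotherapy arm", which is descriptive only. SAP 4.2.3 (sensitivity) and 4.6.1 (subgroups) are both marked not applicable. No stratification by HBsAg is visible in protocol 6.3.
- **Entry (protocol 5.1.3).** The criterion on "Plasma or serum HBsAg concentration" requires more than 100 IU/mL and shows no upper limit.

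**The concern.** Baseline HBsAg can vary widely. The title of SAP Figure 2 limits the optional bepirovirsen group to screening values of at most 3000 IU/mL, which implies that participants above that level can enter. The span from 100 to 3000 alone is log10(30) = 1.48 log10 units. Subtracting baseline removes its influence fully only if the post-baseline value rises one for one with baseline, and nothing in the documents establishes that. Baseline is also a single measurement, so any error in it enters every change value for that participant.

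In a trial of fewer than 20 participants the arms can easily differ at baseline. If baseline is related to log10 change, that difference passes into the estimated treatment difference. A value already collected could correct for it, but the readable plan does not use it in this way.

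**Working it through.** The documents show no figure to reproduce: Part 3 size, allocation, β, the cutoff and the operating characteristics are blacked out.

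**Size.** SAP 1.1.3 equates more than 20% with 4 or more participants. Then 4/N > 0.20 gives N < 20, and 3/N ≤ 0.20 gives N ≥ 15. So N is 15 to 19, if N is the whole of Part 3. I use N = 18 below, split 12:6 where a split is needed (assumed).

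**Chance imbalance.** The difference in mean baseline has SD √(1/n₁ + 1/n₂) in baseline SDs.
- At 12:6 this is √(1/12 + 1/6) = 0.50, so the chance that the arms differ by more than half a baseline SD is 2(1 − Φ(0.5/0.50)) = 32%.
- Over N = 15 to 19 and splits from 1:1 to 3:1, the SD is 0.46 to 0.60.
- A half-SD imbalance shifts the unadjusted difference by rho × 0.5 outcome SDs: 0.15 at rho 0.3 and 0.25 at rho 0.5.

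**Effect of adjusting.** Under normal theory, variance adjusted/unadjusted = (1 − rho²)(N − 3)/(N − 4), where rho is the correlation of baseline log10 HBsAg with maximum log10 change (assumed). At N = 18:

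| rho | calculation | ratio |
|---|---|---|
| 0 | 1.00 × 15/14 | 1.07 |
| 0.2 | 0.96 × 15/14 | 1.03 |
| 0.3 | 0.91 × 15/14 | 0.975 |
| 0.5 | 0.75 × 15/14 | 0.80 |
| 0.7 | 0.51 × 15/14 | 0.55 |

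The ratio equals 1 at |rho| = 1/√(N − 3), which is 0.29 at N = 15 and 0.25 at N = 19. At rho 0 the cost is 12/11 = 1.09 at N = 15 and 16/15 = 1.07 at N = 19.

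**Role of the known β.** With β fixed, the posterior SD of the difference is about β√(1/n₁ + 1/n₂), whatever the residual scatter. For outcome SD 1, β = √6/π = 0.780, giving 0.780 × 0.50 = 0.39. A simulation of 3000 trials at 12:6 (normal baseline, Gumbel residual, total outcome SD 1) gave:

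| rho | sampling SD, unadjusted | sampling SD, adjusted | posterior SD, unadjusted | posterior SD, adjusted, β unchanged | posterior SD, adjusted, β reset to residual scale |
|---|---|---|---|---|---|
| 0 | 0.404 | 0.429 | 0.39 | 0.41 | 0.41 |
| 0.3 | 0.436 | 0.408 | 0.39 | 0.41 | 0.39 |
| 0.5 | 0.477 | 0.375 | 0.39 | 0.41 | 0.36 |

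A baseline term alone does not narrow the reported interval; β must change as well. At rho 0.5, however, the unadjusted posterior SD (0.39) understates the sampling SD (0.477). Repeat runs of this set-up put 95% coverage there at 87% to 88% unadjusted and 96% to 97% with baseline added.

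The simulated variance ratios are (0.429/0.404)² = 1.13 at rho 0, (0.408/0.436)² = 0.88 at rho 0.3 and (0.375/0.477)² = 0.62 at rho 0.5. Both the cost and the gain are larger than under normal theory.

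**The case against.** **The specification is partly hidden.** SAP 4.2.2.4 has blacked-out text before and directly after the model. The SAP's list of tables has a blacked-out entry on page 24, evidently Table 6, which could hold a model specification as Table 8 does for steady state. Protocol 9.4.2 is blacked out at the same analysis, and the Part 3 design and sample-size text is hidden too. This stands: a reader might infer that the plan has no baseline term, but only the readable text can be said to lack one. On the other side, that text reads as a whole model, and the sensitivity-analysis entry is legible and empty.

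**Baseline is already subtracted and rho is unknown.** This also stands. Regression to the mean is weak support when true baselines are widely spread. For example, with an assumed baseline SD of 0.7, measurement SD of 0.1 and change SD of 0.3 (all log10), it contributes |rho| of about 0.1²/(0.7 × 0.3) = 0.05.

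**Unadjusted change is a defensible choice in a small early-phase study.** It is, which is why the adjusted analysis belongs beside the primary one and need not replace it.

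Three stronger readings are tempting but unsupported:
- A reader might infer a loss of power. SAP section 2 and protocol 9.1 test no hypothesis, so there is no power or error rate to lose.
- A reader might infer that imbalance distorts the probability that the mean reaches the cutoff. As visible, that probability concerns a mean, not an arm contrast, and between-arm imbalance does not bias a within-arm quantity.
- A reader might infer that every participant has a baseline. SAP 4.1.3 allows it to be missing; only those who contribute the endpoint must have one.

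**Conclusion.** The point holds in limited form. The readable primary model has no baseline HBsAg term, β is treated as known and no sensitivity analysis is planned. In about 15 to 19 participants, chance baseline imbalance in the treatment difference is thus corrected only by subtraction on the log10 scale. Whether a blacked-out passage already deals with this is for the sponsor to confirm.

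The gain from adjusting is conditional. By the normal-theory formula at N = 18 it is about a 20% reduction in variance at rho 0.5 and 2.5% at rho 0.3, with break-even at |rho| of about 0.25 to 0.29. Below that, adjustment costs up to 7% to 9% across the inferred range of N, or about 13% at rho 0 in the Gumbel simulation with β fixed. All of this rests on assumed correlations, an inferred N and, for the simulation and the 32% figure, an assumed 12:6 split. The case for adjusting is protection against imbalance at small cost, not an assured gain in precision.

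**What to change.** 1. The sponsor confirms whether the blacked-out specification includes baseline HBsAg as a covariate or stratification factor. If it includes a covariate, nothing further is needed here.
2. If there is none, replace the entry in SAP 4.2.3 with a pre-specified baseline-adjusted analysis of the treatment difference: location = α_arm + γ × (baseline log10 HBsAg − overall mean), a vague or weakly informative prior on γ, and β estimated rather than fixed. If β is common to both arms, the difference in location is the difference in means.
3. Report the adjusted posterior mean difference and 95% credible interval beside the unadjusted result. Showing the unadjusted model with β estimated as well would separate the effect of the covariate from that of freeing β.

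The cost is one regression parameter, a prior for β and one table, with no new data. The statistical cost is the variance penalty given above if baseline proves unrelated to log10 change. The choice should be fixed before treatment codes are seen; if Part 3 is already unblinded, the analysis should be labelled post hoc.
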